**Table 2a- Visit Windows for open-label treatment period, Stratum A**

Visit	Target Day, Relative to Day 1 of open-label treatment period	Day Range
HbA1c		
Week -2	99	72- up to first dose of DB
FPG		
Week -16	2	2-21
Week -10	43	22- 71

Week -2	99	72 – up to first dose of DB
---------	----	-----------------------------

**Table 2b - Visit Windows for open-label treatment period, Stratum B**

Visit	Target Day, Relative to Day 1 of open-label treatment period	Day Range
HbA1c		
Week -2	43	22– up to first dose of DB
FPG		
Week -8	2	2–21
Week -2	43	22– up to first dose of DB

### **3.1.6 Handling missing data**

In general, other than for partial dates, missing data will not be imputed and will be treated as missing, with some exceptions specified for certain efficacy variables.

#### **3.1.6.1 Last post-baseline observation carried forward (LOCF)**

In the analysis of change (or percent change) from baseline, as well as response endpoint at Week t LOCF, the Week t measurement will be used. If no Week t measurement is available (subject received rescue medication or discontinued treatment before Week t, or the subject has not discontinued, but the measurement was not taken at Week t), the last post-baseline measurement prior to Week t will be used. Unless specified otherwise, all data prior rescue and/or study treatment discontinuation, will be used for the calculation of LOCF values.

#### **3.1.6.2 Imputation of partial dates**

##### **Concomitant Medication Dates**

Imputation of start dates allows medications for subjects to be classified into the categories of prior, concomitant (or both) for tables. An assessment should be made as to the possibility that the subject's medication could fall into each category given the information available for the dates. If it is possible given the date information that a subject's medication could fall into a given category, then the subjects' medication should be included for tables for that category. If a particular category can be ruled out based on partial or full dates available, then the

subject's medication should be excluded from that category. The following date imputation should accomplish this:

### Start Dates

- If year is missing (or the date is completely missing), set equal to the consent date.
- If year is present and month and/or day are missing then impute as the earliest possible date given the partially entered date.
- If the resulting imputed start date is after a non-missing (i.e. not imputed) end date then set the start date equal to the end date.

### End Dates

- If year is missing (or the date is completely missing) set equal to the most recent database extraction date.
- If the year is known but month and/or day is missing, then set equal to the latest possible date provided it is not before the concomitant med start date (actual or imputed). If it is before the concomitant med start date then set it equal to this date.

### **Adverse Events Dates**

#### Onset Dates

In case of missing dates, prior to assigning the treatment that the subject received at the onset of an AE or at the time of a laboratory assessment, imputation rules will be applied as follows:

- If the onset date for an AE is missing or incomplete, an imputed date will be derived to slot the event to an appropriate analysis period. This derived date will not be reported in summary tables or listings. Every effort will be made to determine the actual onset date for the event or to obtain a reliable estimate for the onset date from the investigator.
- If an onset date is **missing** (or the year is missing), the **derived onset date** will be calculated as the first non-missing valid date from the following list (in order of precedence):
  - First active study medication date
  - Consent date
  - If a valid non-missing date is not available for any of these dates, the derived onset date will be set to missing.
- If an onset date is **incomplete**, the derived onset date will be calculated using the following algorithm:

- Calculate a **surrogate date** as the first non-missing valid date from the following list (in order of precedence):
  - First active study medication date
  - Consent date
  - Visit date corresponding to the visit at which the event was reported
  - If a valid non-missing date is not available for any of these dates, the surrogate date will be set to missing.
- Based on the information provided, set the initial derived date to the earliest possible date. If only a year is provided, set the derived date to January first of that year. If a year and month is provided, set the derived date to the first day of that month.
- If the surrogate date is non-missing then:
  - If the derived date is on or after the surrogate date use the derived date as calculated
  - If the derived date is prior to the surrogate date and the surrogate date is consistent with the partial data provided for the onset date, use the surrogate date as the derived date
  - If the derived date is prior to the surrogate date and the surrogate date is not consistent with the partial data provided for the onset date then set the derived onset date to be the latest possible date based on the partial onset date information provided. If only a year is provided, set the derived date to December 31st of that year. If a year and month is provided, set the derived date to the last day of that month.
- If all dates used to determine the surrogate date are missing, then based on the information provided, set the derived date to the earliest possible date. If only a year is provided, set the derived date to January first of that year. If a year and month is provided, set the derived date to the first day of that month.

### End Dates

A missing or incomplete end date of an AE will be imputed according to the following conventions:

- If an end date is missing, the derived end date will be set to missing
- If an end date is incomplete, set the derived end date to be the latest possible date based on the partial onset date information provided. If only a year is provided, set the derived date to December 31st of that year. If the subject died in the same year, then set the imputed date as the death date. If a year and month is provided, set the derived date to the last day of that month.

## **3.2 Primary efficacy endpoint**

The primary efficacy variable is the mean change from baseline in HbA1c at Week 24.

### **3.3 Secondary efficacy endpoints**

The following secondary efficacy variables will be analysed:

- Mean change from baseline in FPG at Week 24
- Mean change from baseline in 2-hour PPG during a 2-hour MTT at Week 24, only applicable for subjects in China
- Mean change from baseline in total body weight at Week 24
- Proportion of subject achieving a therapeutic glycaemic response, defined as a HbA1c < 7.0% at Week 24

### **3.4 Exploratory efficacy endpoints**

The following exploratory endpoints will be analysed:

- The proportion of subjects who require glycaemic rescue or discontinue study treatment for lack of efficacy at Week 24
- Time to glycaemic rescue or discontinuation for lack of efficacy in the double-blind treatment period
- Mean change from baseline in AUC glucose obtained during MTT at Week 24, only applicable for subjects in China
- Mean percent change from baseline in fasting serum lipids (Total-C, LDL-C, HDL-C, TG) during the double-blind treatment period

### **3.5 Safety variables**

The following safety data will be collected and analysed: AEs/SAEs, AESI, clinical chemistry/haematology parameters, physical examination, ECG and vital sign measurements.

#### **3.5.1 Adverse Events**

All AEs and SAEs occurring during the study will be recorded. Details such a start and stop date of AE, causality, action taken with study medication and outcome will be recorded.

Adverse event data will be categorised according to their onset date as follows:

- Pre-treatment AEs: AE onset date < date of first dose of study medication during the open-label period
- Open-label period treatment emergent adverse events (TEAEs): date of first dose of study medication during open-label period ≤ AE onset date ≤ minimum (date of last dose of study medication during open-label treatment period +4 days, date of first dose of study medication during the double-blind treatment period – 1 day) or minimum (date of last dose of study medication during open-label treatment period +30 days, date of first dose of study medication during the double-blind treatment period – 1 day) if SAE
- Open-label period treatment emergent serious adverse events (TESAEs): date of first dose of study medication during open-label treatment period ≤ SAE onset date ≤ minimum (date of last dose of study medication during open-label treatment period

+30 days, date of first dose of study medication during the double-blind treatment period – 1 day)

- Double-blind period TEAEs: date of first dose of study medication during double-blind treatment period  $\leq$  AE onset date  $\leq$  date of last dose of study medication during double-blind treatment period +4 days or date of last dose of study medication during double-blind treatment period +30 days if SAE
- Double-blind period TESAEs: date of first dose of study medication during double-blind treatment period  $\leq$  SAE onset date  $\leq$  date of last dose of study medication during double-blind treatment period +30 days
- Post-treatment AEs: AE onset date  $>$  date of last dose of study medication during double-blind treatment period +4, and SAE onset date  $>$  date of last dose of study medication during double-blind treatment period +30
- Open-label period treatment emergent hypoglycemia: date of first dose of study medication during open-label period  $\leq$  hypoglycemia onset date  $\leq$  minimum (date of last dose of study medication during open-label treatment period +4 days, date of first dose of study medication during the double-blind treatment period – 1 day) or minimum (date of last dose of study medication during open-label treatment period +30 days, date of first dose of study medication during the double-blind treatment period – 1 day) if SAE
- Double-blind period treatment emergent hypoglycemia: date of first dose of study medication during double-blind treatment period  $\leq$  hypoglycemia onset date  $\leq$  date of last dose of study medication during double-blind treatment period +4 days or date of last dose of study medication during double-blind treatment period +30 days if SAE

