### **6.1      Definition of adverse events**

An AE is the development of an undesirable medical condition or the deterioration of a pre-existing medical condition following or during exposure to a pharmaceutical product, whether or not considered causally related to the product. An undesirable medical condition can be symptoms (e.g., nausea, chest pain), signs (e.g., tachycardia, enlarged liver) or the abnormal results of an investigation (e.g., laboratory findings, electrocardiogram). In clinical studies, an AE can include an undesirable medical condition occurring at any time, including run-in or washout periods, even if no study treatment has been administered.

The term AE is used to include both serious and non-serious AEs.

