### **6.3.3 Variables**

The following variables will be collect for each AE;

- AE (verbatim)
- The date when the AE started and stopped
- Maximum intensity
- Whether the AE is serious or not
- Investigator causality rating against the dapagliflozin and saxagliptin (yes or no)
- Action taken with regard to dapagliflozin and saxagliptin
- Outcome.

In addition, the following variables will be collected for SAEs:

- Date AE met criteria for serious AE
- Date investigator became aware of serious AE
- AE is serious due to
- Date of hospitalisation
- Date of discharge
- Probable cause of death
- Date of death
- Autopsy performed

- Causality assessment in relation to study procedure(s)
- Description of AE.

Maximum intensity will be graded according to the following rating scale:

- Mild (awareness of sign or symptom, but easily tolerated)
- Moderate (discomfort sufficient to cause interference with normal activities)
- Severe (incapacitating, with inability to perform normal activities)

It is important to distinguish between serious and severe AEs. Severity is a measure of intensity whereas seriousness is defined by the criteria in Section 6.2. An AE of severe intensity need not necessarily be considered serious. For example, nausea that persists for several hours may be considered severe nausea, but not a SAE unless it meets the criteria shown in Section 6.2. On the other hand, a stroke that results in only a limited degree of disability may be considered a mild stroke but would be a SAE when it satisfies the criteria shown in Section 6.2.

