### 4.2.5.1 Adverse Events

AEs will be classified by Primary SOC and PT according to the MedDRA. Summaries of AEs will use the version of MedDRA that is current at the time of database lock.

In summaries by SOC and PT, AEs will be sorted by overall decreasing frequency within each SOC and PT. In summaries by PT, AEs will be sorted by decreasing frequency within PT according to the highest of either of the combinational dose group across the study.

Separate pages to capture events of hypoglycaemia are contained within the CRF. Hypoglycaemia or discontinuation due to hypoglycaemia would not be reported on an AE CRF page unless the event fulfilled criteria for an SAE in which case a serious AE (SAE) form would be completed. Hypoglycaemia events that are reported as SAEs will be included in all summaries of AEs or SAEs. Separate summaries will be provided including hypoglycaemia events reported on the special CRF pages.

Analysis of AE will be on treatment-emergent AEs for open-label treatment period and double-blind treatment period, as defined in section [3.5.1](#).

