### **Adverse Events Leading to Discontinuation of Study Medication**

AEs with an onset during the double-blind treatment period reported with an action taken of discontinuation of study medication will be summarised by SOC, PT and treatment group. This summary will include hypoglycaemia events that reported as SAEs. When summarising AEs leading to discontinuation no upper cutoff day windows are applied.

In addition, a subject listing of discontinuation due to AEs will be provided, displaying all events that led to discontinuation that occurred during the study.

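### An adverse event that starts in the lead-in and stops dapagliflozin or placebo after randomisation is left out of the double-blind discontinuation counts; lead-in events that turn serious or worsen depend on an undefined date and on how the record is kept

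*SAP*

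**What the plan says.** **Period assignment.** SAP 3.5.1 opens with "Adverse event data will be categorised according to their onset date as follows". The two double-blind windows begin "Double-blind period TEAEs: date of first dose of study medication during double-blind treatment period" and "Double-blind period TESAEs: date of first dose of study medication during double-blind treatment period". The first is applied to the AE onset date, the second to an *SAE onset date* that the SAP does not define. Seriousness changes only the upper end of a window (4 or 30 days after the last dose). No clause covers an earlier event that worsens.

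**Use of the rule.** SAP 4.2.5.1 carries it into the analyses: "Analysis of AE will be on treatment-emergent AEs for open-label treatment period and double-blind treatment period".

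**Discontinuations.** The relevant part of SAP 4.2.5.1 states that "AEs with an onset during the double-blind treatment period reported with an action taken of discontinuation of study medication will be summarised". It then waives the upper day cutoff for this table but not the onset requirement. A listing covers all events that led to discontinuation during the study.

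**Data collected.** Protocol 6.3.1 collects AEs from the first open-label saxagliptin dose. Protocol 6.3.3 records, for each AE, start and stop dates, one maximum intensity and "Action taken with regard to dapagliflozin and saxagliptin". For SAEs it adds "Date AE met criteria for serious AE". The AE definition in Protocol 6.1 includes "the deterioration of a pre-existing medical condition following or during exposure to a pharmaceutical product".

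**After early termination.** SAP 4.4 keeps the overall AE summary for both periods (including a line for events leading to discontinuation), the SOC/PT tables of TEAEs for both periods, a SOC/PT table of TESAEs for the double-blind period only, the disposition summaries, and AE and SAE listings. SAP Section 6 drops the other planned analyses.

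**The concern.** AEs accumulate for 8 weeks (Stratum B) or 16 weeks (Stratum A) before dapagliflozin or placebo is given, and Protocol 6.3.2 follows them until they resolve or stabilise. Some will be ongoing at Day 1. If such an event later causes a subject to stop randomised drug, that is an outcome of the double-blind period, yet the onset rule files it under open-label saxagliptin, outside the comparison between arms. Protocol 8.5.7 plans a summary of AEs leading to discontinuation for each treatment group without this restriction.

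The table of discontinuations due to AEs can then disagree with two other outputs: the listing of those discontinuations and the disposition table of treatment withdrawals by reason (SAP 4.2.1). Under SAP 4.4, a lead-in event that turns serious after Day 1 and keeps its start date would be in no SOC/PT table of TESAEs. For laboratory data the SAP does test for worsening: Appendix 2 counts a marked abnormality only if it is more extreme than baseline. AEs have no equivalent. The safety report is descriptive and the trial will be small, so a single misplaced serious event or discontinuation would be noticeable.

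**Working it through.** There is no stated figure to reproduce. The check applies the SAP 3.5.1 date rules to hypothetical events.

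**Windows.** Days are counted from the first double-blind dose (Day 1); there is no Day 0 (SAP 3.1.1).

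- Lead-in start: 16 × 7 = 112, so Day −112 in Stratum A; 8 × 7 = 56, so Day −56 in Stratum B.
- Open-label window: from lead-in start to the earlier of (last open-label dose + 4 days, or + 30 if serious) and the day before the first double-blind dose. With continuous dosing the second limit applies, so the window ends the day before Day 1.
- Double-blind window, with the last dose on the Week 24 target day of SAP Table 1 (Day 169): Day 1 to 169 + 4 = Day 173, or to 169 + 30 = Day 199 if serious.

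**Cases.** The results are the same in both strata, because −112 and −56 are both earlier than −20.

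| Event | Date used | Test | Period |
|---|---|---|---|
| Starts Day −20, stops IP Day 40 | −20 | −20 < 1 | Open-label; outside the double-blind discontinuation table |
| Starts Day −20, serious Day 30, *SAE onset date* = AE start | −20 | −20 < 1 | Open-label |
| Same, *SAE onset date* = date serious criteria met | 30 | 1 ≤ 30 ≤ 199 | Double-blind |
| Starts Day −20, worsens Day 30, same record | −20 | −20 < 1 | Open-label |
| Same, new record opened at worsening | 30 | 1 ≤ 30 ≤ 173 | Double-blind |

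Only the first row follows from the text without a further assumption. Waiving the upper cutoff does not help, because the event fails the lower bound. Rows 2 to 5 show that the serious case turns on an undefined term and the worsening case on a recording convention.

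**Possible size.** The documents give no AE rates. The assumptions are that 5–20% of randomised subjects have an AE ongoing at Day 1, and that 5–10% of those AEs worsen, turn serious or stop IP.

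- Planned trial: 342 × 0.05 = 17.1 and 342 × 0.20 = 68.4 subjects with an ongoing AE. Affected: 17.1 × 0.05 = 0.9 to 68.4 × 0.10 = 6.8, so about 1–7.
- Planned outside China: 23 per arm × 3 = 69. Affected: 69 × 0.05 × 0.05 = 0.17 to 69 × 0.20 × 0.10 = 1.38, so about 0.2–1.4.

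The second line is closer to the trial as it will finish, because SAP 4.4 closes the study without recruiting in China. The actual number randomised is not given.

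**The case against.** The case on the other side has force on several points.

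- **The discontinuation table itself is no longer planned.** SAP 4.4 does not list it. This stands, but 4.4 keeps a discontinuation line in the overall AE summary for the double-blind period, and the treatment-emergent rule governs that line too.
- **Becoming serious.** The SAP uses a different term for TESAEs than for TEAEs, and the protocol collects the date on which serious criteria were met. Reading *SAE onset date* as that date is reasonable and puts the event in the double-blind table. A reader might infer that the SAP excludes every such event; it does not say so. What stands is that the term needs a definition.
- **Worsening.** The AE definition covers deterioration, and Protocol 6.3.6 has aggravated physical findings reported as AEs. If sites open a new record, the event has a double-blind onset. The eCRF instructions are not among the documents. What stands is that no stated rule requires a new record for an ongoing lead-in AE.
- **Events do not disappear.** A reader might infer that they are lost altogether. The AE and SAE listings show them whatever their onset, disposition shows treatment withdrawals by reason, and the full SAP tabulates laboratory worsening separately. The loss is from double-blind summary tables.
- **Bias.** A reader might infer that harm is understated in the dapagliflozin arms. Protocol 6.1.1 names urinary and genital infections, volume depletion and similar events as being of special interest, but nothing in the documents shows that ongoing lead-in cases are aggravated by dapagliflozin. A recurrent infection may well be a new episode with its own onset.

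**Conclusion.** The point holds in a limited form. The onset restriction on AEs leading to discontinuation is a wrong rule rather than a missing detail: it excludes by its own wording a lead-in event that stops randomised drug. The two related gaps are conditional, one on how *SAE onset date* is read and the other on whether a worsening AE stays on its existing record.

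The number of subjects affected cannot be calculated from the documents. The ranges of 1–7 (342 planned) and 0.2–1.4 (about 69 planned outside China) rest wholly on the assumed rates, and they pool all three routes. The larger range should not be read as the expected loss, since recruitment in China will not take place. A difference between arms is plausible but not documented. The change is still worth making, because the remaining report is small and descriptive and its counts should agree with its own listings and disposition table.

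**What to change.** 1. **Discontinuations.** In SAP 4.2.5.1 and the overall summary in 4.4, count every AE whose action taken is discontinuation of double-blind dapagliflozin or placebo, whatever its onset date. Neither is given before Day 1, so this action can only belong to the double-blind period. It relies on the action-taken field separating dapagliflozin from saxagliptin, which should be confirmed.
2. **Serious events.** In SAP 3.5.1, define *SAE onset date* for period assignment as the collected "Date AE met criteria for serious AE". Count an event that qualifies this way among the double-blind TEAEs as well, so that the TESAE and TEAE rows agree.
3. **Worsening.** State that an AE recorded as worsening on or after the first double-blind dose is double-blind treatment-emergent. Worsening inside an existing single record cannot be dated retrospectively, because Protocol 6.3.3 lists only one maximum intensity. The SAP should acknowledge that limit.

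The cost is SAP wording and minor programming. Items 1 and 2 use fields already collected. An instruction to sites to open a new record could apply only to entries still to come. Double-blind counts would rise slightly.
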